11.2 Treatment-related Mortality

All deaths in the absence of relapse of the primary malignancy will be considered treatment

CONFIDENTIAL

This document is confidential. Do not disclose or use except as authorized.

related mortality. The cumulative incidence of treatment related mortality at 50 days will be measured.

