1.3 Secondary Objectives

1. To evaluate the days to neutrophil recovery (the first of 3 days of ANC >500)
2. To evaluate the days to platelet recovery (platelet count >20K unsupported)
3. To evaluate the treatment-related mortality (the number of non-relapse related deaths in the first 50 days of starting treatment)
4. To evaluate the transfusion support (the number of red blood cell and platelet transfusions needed in the first 50 days of treatment)
5. To determine if certain genetic profiles of the leukemia predict for better response (optional correlate)

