11.5 Evaluation of Response

All participants included in the study must be assessed for response to treatment, even if there are major protocol treatment deviations or if they are ineligible. Each participant should be assigned one of the following categories: 1) complete remission, 2) complete remission without neutrophil or platelet recovery, 3) persistent disease, 4) early death from leukemia 5) early death from toxicity, or 6) unknown (not assessable, insufficient data). World Health Organization (WHO) criteria will be used to assess response. Patients will be assessed for complete remission or complete remission without platelet recovery per WHO criteria. (43) Patients who experience toxicity but die with persistent leukemia will be classified as 3) death of persistent disease.

Morphologic Complete Remission (CR):

Defined as morphologic leukemia-free state, including <5% blasts in Bone Marrow aspirate with marrow spicules, no persistent extramedullary disease, ANC >1000/mm³ and platelet count >100,000/mm³.

Morphologic Complete Remission without neutrophil (CRi) or platelet recovery (CRp):

Defined as CR with the exception of neutrophil count < 1,000/mm³ (CRi) or platelet count < 100,000/mm³ (CRp).

Persistent Disease:

Greater than 5% blasts in the marrow.

CONFIDENTIAL

This document is confidential. Do not disclose or use except as authorized.

Recurrence/morphologic relapse:

Defined as reappearance of >5% blasts in the bone marrow, not attributable to any other cause, *after* the documentation of complete remission (CR)

Early death from leukemia:

Defined as death within 50 days of treatment attributed to persistent leukemia.

Early death from toxicity:

Defined as death within 50 days of start of treatment attributed to therapy in the absence of leukemia.

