13. STATISTICAL CONSIDERATIONS

Primary objective

This is a single arm study to evaluate the efficacy of lenalidomide in combination with reinduction chemotherapy (mitoxantrone/etoposide/cytarabine) for patients with relapsed or refractory AML.

Sample size

The primary endpoint is complete remission (CR) and CRp after MEC+lenalidomide. A 45% complete remission rate will be considered clinically significant. The response evaluation will be assessed after the first (and only) cycle of treatment. There is no retreatment as a part of this protocol. We will plan to evaluate patients who receive the study treatment; we will plan to replace up to 2 patients who are not able to complete the ten days of therapy.

A two-stage design is considered here. A total number of 40 patients is needed in order to detect a 20% response rate increase, assuming the null hypothesis is 25%, with a 90% power and 9% one-sided type I error rate. The study will be reevaluated if 4 or fewer responses out of 18 patients are observed and the treatment will be declared inactive if fewer than 14 responses are seen in the total 40 patients. Factors during treatment, such as the rate of treatment completion, may be considered in evaluating any responses. The probability of stopping at the first stage is 0.52, if the true response rate is 25%.

We chose this study design over other possible phase II study designs, including randomized phase II designs, because it is powered toward identifying a clinically significant improvement in response (20% increase compared to historical rates); a smaller randomized study may be underpowered to identify the true response rate.

Primary analysis

The rate of CR+CRp will be calculated along with the corresponding 90% two-stage exact binomial CI.

The analyses for secondary objectives will be descriptive in nature. Proportion of patients with ANC recovery/platelet recovery (as defined in Section 11.1) will be reported, along with median days to counts recovery. Total transfusion requirements will be reported as the median and range of each blood product. Cumulative incidence of treatment related mortality (defined in Section 11.2) will be estimated using relapse and early death from relapse as competing risks. Overall survival and Relapse-free survival (defined in Section 11.3) will be estimated using the Kaplan-Meier method.

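### Day-50 treatment-related mortality is not cleanly defined: Section 11.2 can count leukemia deaths in patients who never remit, and Section 13 can drop toxic deaths before Day 10

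*Combined protocol and SAP*

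**What the plan says.** - **Section 11.2** sets the rule: "All deaths in the absence of relapse of the primary malignancy will be considered treatment" related mortality, reported as a cumulative incidence at 50 days. Section 1.3 gives the objective as "the number of non-relapse related deaths in the first 50 days of starting treatment".
- **Section 11.5** describes relapse as follows: "Defined as reappearance of >5% blasts in the bone marrow, not attributable to any other cause". It adds that this must come after CR has been documented. It does not say whether that CR must be achieved on this study.
- **Section 11.3** also defines relapse, as morphological evidence of the original malignancy. It states no prior-CR condition, though it speaks of recurrent malignancy.
- **Section 11.5** has its own death categories. The one for leukemia deaths reads "Defined as death within 50 days of treatment attributed to persistent leukemia". The toxicity category is narrower, because it requires that no leukemia be present: "Defined as death within 50 days of start of treatment attributed to therapy in the absence of leukemia". For mixed cases: "Patients who experience toxicity but die with persistent leukemia will be classified as 3) death of persistent disease".
- **Section 13** gives the analysis: "Cumulative incidence of treatment related mortality (defined in Section 11.2) will be estimated using relapse and early death from relapse as competing risks".
- **Section 13**, in its closing paragraph before 13.1.1, excludes from the analyses, and replaces, participants who do not complete the 10 days. Its sample-size paragraph plans to replace up to 2 patients. Section 13.1.1 keeps all participants evaluable for toxicity from first treatment.

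**The concern.** Section 11.2 sorts deaths by whether relapse occurred, whereas 11.5 sorts them by cause and by presence of leukemia. The two agree for a patient who remits. They can disagree for a patient who never does, because that patient may have no relapse to record. Section 13 does not settle the matter: it adopts the 11.2 definition and then uses a competing-risk term that the protocol does not define.

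The exclusion of non-completers is a second problem and acts in the opposite direction. A patient who dies of toxicity before Day 10 has not completed therapy, so the exclusion can remove exactly the event that TRM is meant to count.

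Day-50 TRM is a named secondary safety objective. Two analysts following this text could report different figures from the same data.

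**Working it through.** The documents state no TRM figure for this trial, so there is none to reproduce. The check sets the definitions side by side and then sizes each effect.

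**Step 1. How each section treats a death by Day 50**

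| Death | 11.2, using the 11.5 relapse definition | 11.5 category |
|---|---|---|
| Primary refractory, never in CR, dies of leukemia | TRM | Early death from leukemia |
| Enrolled in relapse, no CR on study, dies of leukemia | TRM if the CR must be on study; arguably not if an earlier CR counts | Early death from leukemia |
| Primary refractory, never in CR, toxicity with persistent leukemia | TRM | Persistent disease |
| Attributed to therapy, no leukemia | TRM | Early death from toxicity |
| Attributed to therapy, no relapse, leukemia status not documented | TRM | Not settled by the text |

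The last row is realistic. Section 10.2 places the first required post-treatment marrow at count recovery or Day 35 (±3 days), and Section 2.4.1 reports a Phase I median of 30 days to neutrophil recovery.

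If early death from relapse in Section 13 means early death from leukemia, Section 13 agrees with 11.5 but not with the 11.2 definition it cites. If it means death after relapse, the first row has no competing-event category.

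**Step 2. Upper bound on the patients at issue**

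Inputs: N=40, null rate 25% and target rate 45% (Section 13); 14 responders among 36 in Phase I (Section 2.4.1).

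- Non-responders at 25%: 40 × (1 − 0.25) = 30.
- Non-responders at 45%: 40 × (1 − 0.45) = 22.
- Phase I: 36 − 14 = 22, and 22/36 = 61.1%.

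These count everyone without a response. They are not the number of deaths reclassified.

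**Step 3. Effect of each reclassified leukemia death**

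With no censoring before Day 50, the cumulative incidence is the proportion of 40, so each death adds 1/40 = 2.5 points. As an illustration, assume 4 deaths that are TRM on either reading (4/40 = 10%). With 0, 1, 2 or 4 leukemia deaths without CR, literal 11.2 gives 10%, 12.5%, 15% or 20%. Treating those deaths as competing events gives 10% throughout. All these death counts are assumptions. Phase I lists 4 deaths in 36 patients (11.1%): one sepsis, one infection, two respiratory failure. None is listed as due to leukemia.

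**Step 4. Effect of excluding early toxic deaths**

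Let t be the TRM deaths among the 40 analysed, and r the excluded and replaced patients who died of toxicity before Day 10. Then

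understatement = (t + r)/(40 + r) − t/40.

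| r | t = 0 | t = 4 |
|---|---|---|
| 0 | 0 | 0 |
| 1 | 1/41 − 0 = 2.4 points | 5/41 − 4/40 = 12.2% − 10.0% = 2.2 points |
| 2 | 2/42 − 0 = 4.8 points | 6/42 − 4/40 = 14.3% − 10.0% = 4.3 points |

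The range t = 0 to 4 is assumed. The row r = 2 uses the planned number of replacements.

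**The case against.** **The intent is mostly visible.** Beside relapse, a competing risk that meant only death after relapse would be redundant, so the term in Section 13 probably means leukemia death. The objective in Section 1.3 can also be read by cause of death. This is a fair account of intent and it stands. It does not repair the text, because Section 13 still refers to 11.2 for the definition.

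**The conflict depends on which relapse definition is used.** On the 11.3 wording, persistent morphologic leukemia might count as relapse, and such a death would not be TRM. That is arguable. It would leave the protocol with two incompatible relapse definitions, which also needs correcting.

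**The reach is narrower than it looks.** A reader might infer that all 22 to 30 expected non-responders are affected. The documents do not support that. Section 3.1.1 admits patients in first relapse or higher as well as primary refractory patients. Because 11.5 does not require the CR to be on study, patients enrolled in relapse may already satisfy it. The enrolment mix is not given, and only those who die by Day 50 matter.

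**Aligning TRM with 11.5 alone would create a new gap.** Early toxic deaths will often lack documented leukemia status and could be lost from TRM. This is correct, and the fix must cover it.

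**Other sections already protect the denominator.** Section 11.2 speaks of all deaths, and 13.1.1 keeps every participant evaluable for toxicity. That favours an all-treated denominator, but the Section 13 exclusion makes no exception for TRM.

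**Conclusion.** The point holds and is minor. Under the 11.5 relapse definition, Section 11.2 can count a never-remitter's leukemia death by Day 50 as TRM, most clearly in primary refractory patients, and Section 13 does not resolve the conflict. The size is 2.5 points per death at N=40, assuming no censoring before Day 50. The number of such deaths is unknown and may be zero.

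The exclusion rule can understate TRM by about 2.2 to 2.4 points for one toxic death before Day 10, given 0 to 4 TRM deaths among the other 40. A reader might take 4.8 points, the largest result with two replaced patients, as the maximum. It is not a firm one, because the exclusion sentence states no cap. Nor do the documents show that reported TRM will be too high or too low overall: the two effects are opposed and neither count is known.

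TRM is descriptive. The CR+CRp analysis, the two-stage rule and the 3-of-10 safety hold do not depend on these definitions.

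**What to change.** 1. Use one relapse definition in 11.3 and 11.5, and state whether the prior CR must be achieved on study.
2. In 11.2 and Section 13, replace early death from relapse with two named competing events: relapse, and death attributed to persistent leukemia, including deaths that 11.5 assigns to persistent disease. State that a death attributed to therapy with leukemia status not documented, for example before the first post-treatment marrow, counts as TRM. Use the attribution that Section 7.3.5 already requires.
3. Estimate TRM in all patients who received any study treatment, whether or not they completed 10 days or were replaced.
4. Report all-cause Day-50 mortality beside TRM, because 11.5 assigns toxic deaths with persistent leukemia to disease.

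The cost is wording in 11.2, 11.3, 11.5 and 13. Response categories and death attribution are already required, so no new assessment is needed. Two limits remain: the result leans on the investigator's attribution of cause, and toxic deaths with documented persistent leukemia stay outside TRM. The all-cause figure keeps both visible.

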11.3 Relapse-Free and Overall Survival

Both overall survival and relapse-free survival will be assessed at 45 days after the start of study treatment, as well as over the 3 year planned follow-up period. Overall survival is defined as time from diagnosis of disease until date of death or censored on the last known date alive if patients are still alive. Testing for recurrent malignancy in the blood, marrow or other sites will be used to assess relapse after treatment. Relapse is defined by morphological evidence of the original malignancy consistent with pre-treatment features. Minimal residual disease is defined by the sole evidence of malignant cells by flow cytometry, or fluorescent in situ hybridization (FISH), or polymerase chain reaction (PCR), or other techniques, in absence of morphological or cytogenetic evidence of disease in blood or marrow. Since the frequency of testing for minimal residual disease is highly variable, and the sensitivity is highly variable among laboratory techniques, evidence of minimal residual disease will not be sufficient to meet the definition of relapse in the context of this study. Relapse free survival is defined from time of diagnosis to disease relapse or death whichever occurs first or censored on the last known date of free from disease relapse.

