Version: February 27, 2019

DF/HCC Protocol #: 16-574

NCT #: NCT03118466

TITLE: Phase 2 Study of Mitoxantrone, Etoposide, and Cytarabine (MEC) plus Lenalidomide for the Treatment of Adult Patients with Relapsed or Refractory Acute Myeloid Leukemia

Coordinating Center: Massachusetts General Hospital
Program for the Coordination and Oversight of Research
Protocols (PCORP)

***Principal Investigator (PI):** [name]
Massachusetts General Hospital Cancer Center

Other Investigators: [name]
Dana Farber Cancer Institute

[name]
Beth Israel Deaconess Medical Center

[name]
University of Virginia

Responsible Research Nurse(s):

[name] and [name]
Massachusetts General Hospital

10

Responsible Data Manager:

[name]
Massachusetts General Hospital

1

Other Agents:	Lenalidomide	Supplied by Celgene
	Mitoxantrone	Commercial Supply
	Etoposide	Commercial Supply
	Cytarabine	Commercial Supply

Study IND: 133806

Protocol Type / Version # / Version Date: Original/ Version 2.2 February 27, 2019

SYNOPSIS AND SCHEMA

Title:

Phase 2 Study of Mitoxantrone, Etoposide, and Cytarabine (MEC) plus Lenalidomide for the treatment of Adult Patients with Relapsed or Refractory Acute Myeloid Leukemia (AML)

Primary Objective:

The primary objective of this study is to assess rates of complete remission (CR) and rates of complete remission with incomplete platelet recovery (CRp) after treatment with mitoxantrone, etoposide, cytarabine (MEC) and lenalidomide.

Secondary Objectives:

1. To evaluate the days to neutrophil recovery (the first of 3 days of ANC >500).
2. To evaluate the days to platelet recovery (platelet count >20K unsupported).
 3. To evaluate the treatment-related mortality (the number of non-relapse related deaths in the first 50 days of starting treatment.)
4. To evaluate the transfusion support (the number of red blood cell and platelet transfusions needed in the first 50 days of treatment).
5. To determine if certain genetic profiles of the leukemia predict for better response (optional correlative study)
6. To evaluate relapse and survival following treatment with MEC and lenalidomide.

Study Design:

This is a single arm Phase 2 study which consists of determining the overall response rate of Lenalidomide + MEC in relapsed or refractory AML patients. A 45% complete remission rate will be considered clinically significant.

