10.4 Long Term Follow Up

Participants will be followed for at least 50 days after the start of protocol treatment to assess for response to treatment and adverse events. At the completion of the study treatment, participants will be followed for relapse and overall survival outcomes for a total of 3 years from the start of treatment. These outcomes should be assessed at approximately 3 months after treatment, and then approximately every six months until the 3 year follow-up has been reached.

Patients removed from the study treatment early, for instance patients with refractory disease who go onto another therapy within 45 days of the study therapy, and will continue to be followed for relapse and survival for up to three years following initiation of study treatment.

Participants removed from protocol therapy for unacceptable adverse event(s) will be followed until resolution or stabilization of the adverse event. They will then also be followed at the above approximate intervals for relapse and survival outcomes.

Baseline evaluations are to be conducted within 21 days prior to the start of protocol therapy.

Assessments must be performed prior to administration of any study agent. Study assessments should be administered within \pm 3 days of the protocol-specified date, unless otherwise noted.

Table 6. Required Study Data.

	Pre-treatment (within 21 days)	Weekly (+/- 3 days)	Count recovery or Day +35 (+/- 3 days)	Day +38	Day +45 +/- 3 days
Medical History and Physical Exam	X				
CBC with diff	X	X (Diff optional)			X
Comprehensive chemistry with renal and liver functions ¹	X	X			X
ABO/Rh	X				X
Bone marrow biopsy and aspirate ²	X		X		X
Informed Consent	X				
History and physical	X	X			X
Performance Status	X				
EKG	X				
MUGA or ECHO	X				

CONFIDENTIAL

This document is confidential. Do not disclose or use except as authorized.

Chest x-ray	X				
Toxicity assessment ⁴	X	ongoing throughout			
Enroll in REMS	X				
Pregnancy Test Child Bearing Female	X			X	
Optional Research Studies	X ⁵	b	X		

¹ Chemistry testing to include creatinine, eGFR, BUN, potassium, sodium, chloride, HCO3, glucose, magnesium, phosphorus, calcium. Liver function testing to include ALT, AST, total bilirubin, alkaline phosphatase, albumin.

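### Overall survival and relapse-free survival are timed from diagnosis rather than from study treatment, so overall survival is overstated and relapse-free survival does not measure the regimen

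*Combined protocol and SAP*

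**What the plan says.** Section 11.3 defines the two endpoints as follows.

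- OS: "Overall survival is defined as time from diagnosis of disease until date of death or censored on the last known date alive".
- RFS: "Relapse free survival is defined from time of diagnosis to disease relapse or death whichever occurs first", otherwise censored when last known to be free of relapse.

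The same section opens by saying that both endpoints "will be assessed at 45 days after the start of study treatment" and over the 3-year follow-up. On relapse it says: "Testing for recurrent malignancy in the blood, marrow or other sites will be used to assess relapse after treatment".

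Section 13 gives the estimator: "Overall survival and Relapse-free survival (defined in Section 11.3) will be estimated using the Kaplan-Meier method". It mentions neither delayed entry nor another time origin. It also says: "The analyses for secondary objectives will be descriptive in nature".

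The objective served is item 6 of the synopsis secondary objectives: "To evaluate relapse and survival following treatment with MEC and lenalidomide". Section 1.3 lists only the first five items and omits it. Section 10.4 sets the follow-up clock: "participants will be followed for relapse and overall survival outcomes for a total of 3 years from the start of treatment". The synopsis (Study Duration) and Section 5.6 also count follow-up from the start of treatment.

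Section 3.1.1 admits patients with primary refractory disease after at least one induction cycle, or in first or later relapse.

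**The concern.** Every patient has been diagnosed, treated and found refractory or relapsed before entering. Sections 4.1 and 4.3 cancel the registration of anyone who does not receive protocol therapy, and Section 13 excludes those who never start. No analysed patient can die between diagnosis and Day 1. An ordinary Kaplan-Meier curve that starts at diagnosis still counts that interval as survival.

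The curve would then mix survival before the study with survival after the regimen, while the objective asks only about the second. The protocol also uses two clocks: follow-up and the 45-day assessment run from treatment start, and the endpoint definitions run from diagnosis. A reader who set the reported OS beside the MEC survival figures in Section 2.2 could see an advantage that owes nothing to lenalidomide.

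**Working it through.** **The plan's own figures.** The documents give no target, power or sample size for OS or RFS. The figures that exist concern CR+CRp. For the two-stage rule (18 then 22 patients, continue with 5 or more responses, active with 14 or more of 40), the probability of declaring activity is the sum over x = 5 to 18 of b(18, x, p) × P(Bin(22, p) ≥ 14 − x). This gives 0.0949 at p = 0.25 and 0.9042 at p = 0.45. The first-stage stopping probability is P(Bin(18, 0.25) ≤ 4) = 0.5187. These agree with the stated 9%, 90% and 0.52 at their rounding. No survival time enters them.

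**OS: direction.** Let T be time from Day 1 to death and L the time from diagnosis to Day 1. Section 11.3 measures L + T, and the objective concerns T. Because L is positive and contains no deaths, L + T exceeds T for every patient.

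**OS: size.** For a fixed lag, median(L + T) = L + median(T). Inputs:

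- Median(T): 5 months, cited for two MEC studies in Section 2.2; a third reports 104 days, or 104/30.44 = 3.42 months. That section does not state the time origin, so a treatment origin is an assumption.
- L: not in the documents. All values below are assumptions. One month = 30.44 days, so 7 days = 0.23 and 21 days = 0.69 months.

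| Assumed L | Median OS, true 5.0 months | Ratio | Median OS, true 3.42 months |
|---|---|---|---|
| 7 days | 5.2 | 1.05 | 3.7 |
| 21 days | 5.7 | 1.14 | 4.1 |
| 2 months | 7.0 | 1.4 | 5.4 |
| 6 months | 11.0 | 2.2 | 9.4 |
| 12 months | 17.0 | 3.4 | 15.4 |

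If T is also assumed exponential with a 5-month median, 12-month OS from treatment is 0.5^(12/5) = 19%. From diagnosis it is 0.5^(10/5) = 25% with a 2-month lag, 0.5^(6/5) = 44% with 6 months, and 100% with 12 months.

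Lags will differ between patients. With half at 2 months and half at 12, 12-month OS is 0.5 × 0.25 + 0.5 × 1 = 62.5%. The median solves 0.5 × 0.5^((t−2)/5) + 0.5 × 0.5^((t−12)/5) = 0.5, giving t = 13.6 months.

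**RFS: two readings.**

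1. Relapse means relapse after study treatment. The testing sentence in 11.3 and the relapse definition in 11.5 (reappearance of blasts after documented CR) support this. RFS then includes L, as OS does.
2. The definition is read literally, from diagnosis to relapse. A patient enrolled in relapse has then already had the event before Day 1, and the recorded time describes earlier therapy.

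Neither reading measures relapse-free time after the regimen. Section 11.3 also does not say whether RFS is limited to patients who remit, or how those who never remit are handled.

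**The case against.** **Diagnosis may mean the current relapsed or refractory state.** The text does not say so, but the reading is possible. Some time before Day 1 would still be counted, so the direction for OS is unchanged. The excess could be only days, as the 7-day row shows. This part of the objection stands: the effect may be small.

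**The consequence is limited.** This also stands. The endpoints are descriptive, item 6 is absent from Section 1.3, and no survival test or comparison is planned.

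A reader might also infer four stronger points that the documents do not support.

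- *Both endpoints are biased upward.* This is certain for OS only. For RFS it holds under the first reading; under the second, the event falls before Day 1.
- *OS at 45 days would be 100% by construction.* That would follow for 45 days after diagnosis if every lag were 45 days or more. Section 11.3 plans the assessment at 45 days after treatment start. The clash of clocks is real, but no 45-days-from-diagnosis estimate is planned.
- *The documents supply the lag.* They do not. The 21 days in Sections 3.1 and 10.1 is the limit of the screening window. The 2 months in Section 9.1.1.1 limits an optional mutation test. The 90 days in Section 3.1.10 applies only after transplant.
- *The relapse event is left open because 11.3 and 11.5 differ.* Section 13 points RFS to 11.3, which covers blood, marrow and other sites and does not require prior CR. Aligning the two sections would be tidy, but it is a secondary matter.

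**Conclusion.** Wrong as written. For OS the direction is certain: the definition counts time that cannot contain a death, so it overstates survival following treatment. It also conflicts with the treatment-start clock in the synopsis, Sections 5.6 and 10.4, and the opening of 11.3. For RFS the diagnosis origin fails on either reading, but a direction of bias cannot be asserted without choosing one.

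The size is unknown. Under the illustrative 5-month median the excess runs from about 0.2 months (7-day lag) to 12 months (12-month lag): small if diagnosis means the current disease state, large if it means original diagnosis. The lags and the treatment origin of the cited medians are assumptions; the 12-month survival percentages and the mixed-lag median also assume exponential survival.

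This should be fixed, but it does not threaten the trial's main conclusion. The CR+CRp analysis, the 40-patient sample size, the stage boundaries and the safety hold do not use either endpoint.

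**What to change.** Amend Section 11.3.

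- **OS:** from the first day of protocol treatment to death from any cause, censored at the last date known alive.
- **RFS:** choose one. (a) From documented remission to relapse or death among responders, stating whether CRp and CRi count as remission. (b) If all patients are to be included, call it event-free survival, start it on the first day of protocol treatment, and count persistent disease as an event along with relapse and death.
- **Time from diagnosis:** if it is also reported, say which diagnosis is meant and use Kaplan-Meier with delayed entry at Day 1.

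Section 13 can keep its reference to 11.3, with the endpoint name changed if (b) is chosen and the delayed-entry method added if needed. No new assessments are required, because treatment start and the marrow examinations are already part of the study procedures. Making the change before analysis also avoids choosing the origin after results are known.

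The cost is that reported survival becomes shorter. Option (a) would rest on few patients: 40 × 0.25 = 10 at the null response rate and 40 × 0.45 = 18 at the target rate.
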